In this pilot study, 24 participants will be accepted from our referral sources in the department of Neurology and Physical Medicine. There will be 2 measurement periods before the training starts, separated by 3-14 days in order to establish baseline word-finding performance on selected trained and untrained word lists. Following the lead-in period, subjects will participate in a cross-over design training period to compare the two tDCS conditions (1mA anodal vs. sham). The training portion of the study will occur over a total of 3 weeks. During that time, subjects will attend five consecutive, 60-minute training sessions under treatment condition one (anodal vs. sham tDCS), followed by a 1 week rest interval, and then another five consecutive sessions of training under treatment condition two. Order of training word lists and tDCS stimulation condition will be counterbalance across participants. Subjects will undergo four additional evaluations throughout the course of the study, two of which will occur immediately after each of the training conditions (discharge), and the other two of which will occur 1 week after each training condition (follow-up). All study procedures will be administered or supervised by the research coordinator or another licensed Speech-Language Pathologist. All visits will be conducted in the clinical robotics and non-invasive brain stimulation suite at the Feinstein.

Lead-in Period

- Week 1, Visit 1 (approximately 60 minutes)
 - Baseline outcome measures
 - Medical screening
 - Consent
- Week 2, Visit 2 (approximately 60 minutes each)
 - Baseline outcome measures

Training Period Phase I

- Week 3, Visit 3-6 (approximately 60 minutes)
 - 20 min of stimulation condition 1 (sham or anodal tDCS) and 20 min of computerized word-picture matching therapy
- Week 3, Visit 7 (approximately 90 minutes)
 - 20 min of stimulation condition 1 (sham or anodal tDCS) and 20 min of computerized word-picture matching therapy
 - Condition 1 discharge outcome measures

Follow Up Testing Phase I

- Week 4, Visit 8 (approximately 60 minutes)
 - Condition 1 follow-up outcome measures

Training Period Phase II

- Week 5, Visit 9-12 (approximately 60 minutes)
 - 20 min of stimulation condition 2 (sham or anodal tDCS) and 20 min of computerized word-picture matching therapy
- Week 5, Visit 13 (approximately 90 minutes)
 - 20 min of stimulation condition 2 (sham or anodal tDCS) and 20 min of computerized word-picture matching therapy

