This self-administered computerized anomia treatment was reported on in a previous study, and demonstrated to be helpful in improving naming accuracy of individuals with aphasia (4). Subjects are asked to perform a 20-minute picture-word matching task following receipt of either sham or anodal tDCS.

Randomization

A single-subject cross-over design will be used to compare two tDCS conditions (1mA anodal vs. sham). The order of anodal or sham stimulation will be counterbalanced across participants, and determined using a random number generator.

Blinding

This is a double blind study. The tDCS device will be covered such that the administrator will code each stimulation condition as either switch “up” or switch “down,” but will remain blinded to which code is anodal vs. sham stimulation. In this way, all investigators interacting with patients will remain unaware of stimulation condition. For the sham condition, the stimulation automatically ramps down after 30 seconds because the perceived sensation of tDCS on the skin has been reported to fade after this period (21). Consequently, participants will also stay blinded to stimulation condition.

Statistical Considerations and Data Analysis

SPECIFIC AIM 1: To evaluate whether anodal tDCS preceding aphasia therapy significantly improves picture naming in individuals with post-stroke aphasia.

Methods to address specific aim 1: A Wilcoxon signed-rank test will be used to compare naming accuracy scores pre and post anodal tDCS condition across participants.

SPECIFIC AIM 2: To compare naming performance between intervention conditions (tDCS and sham stimulation).

Methods to address specific aim 2: If neuromodulation preceding treatment is effective for promoting recovery in language impairment, as it is in robotic hemiplegia treatment, we expect the improvement in naming accuracy to be greater following anodal tDCS compared with sham tDCS. This will be examined with a 2x2 repeated measures ANOVA for both treated and untreated items with stimulation type (A-tDCS,S-tDCS) and time (T1, T2) as factors.

SPECIFIC AIM 3: To compare naming performance between severity groups (high vs. low functioning aphasia as determined by admission Western Aphasia Battery scores (WAB)).

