Methods to address specific aim 3: This will be examined with a 2x2 repeated measures ANOVA with change in naming performance in each stimulation condition (change in naming performance A-tDCS vs. S-tDCS) and severity level (high vs. low functioning aphasia).

Protection of Human Subjects

RISKS TO SUBJECTS

Human Subject Involvement and Characteristics: We anticipate enrolling 12 human subjects. Inclusion and exclusion criteria are stated above in the Research Design and Methods section.

Sources of Material: Sources of research material will be the hospital records providing demographic and medical information including CT or MRI imaging studies, and clinical examinations performed at outpatient facilities run by the Department of Physical Medicine and Rehabilitation of the North Shore University Hospital (NSUH) and LIJ Medical Center (LIJMC), or copies of medical records from outside hospitals provided by participants.

Potential Risks:

tDCS Risks: tDCS is a safe technique that poses a non-significant risk to participants. The safety of this technique has been addressed and tested by multiple researchers (16, 18, 20, 33-34) who have concluded that tDCS, as applied in a manner similar to our proposed protocol has no long-term negative side effects. More than 30 research studies involving hundreds of participants have been published using tDCS. Hundreds more participants have undergone tDCS for unpublished pilot research. No undesirable or long-lasting effects have been reported, nor have any participants reportedly abandoned a study due to discomfort.

Researchers at the National Institute of Neurological Disorders and Stroke (NINDS) conducted a safety study on tDCS, investigating 20-minute sessions of 1 mA and 2 mA current stimulation with healthy controls (n=103) (20). No negative effects were identified. Nitsche and colleagues (2004) found no measurable structural changes in brain tissue due to tDCS (23). Additionally, studies have shown that tDCS can be used safely in stroke patients (11, 18, 34-37). Thus, a growing body of research from different laboratories has shown that tDCS is a safe, non-invasive and painless technique for modulating neural excitability, with measurable but only transient effects. The protocol described here uses stimulation levels that fall well within safety limits established by basic research investigating neural tissue damage, as well as

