After a discussion about the study with a potential subject and/or a potential subject's legally authorized representative (LAR)/next of kin, interested parties will be given a copy of the consent form by one of the study investigators. The investigator will review and explain the consent form. All information about the study will be provided. Ample time will be given for individuals to ask questions regarding participation and to have questions answered prior to signing the consent form. If so desired, those interested will be given a copy of the consent form so that they may have the opportunity to discuss participation further with family and/or advisors. Only those investigators listed in the study protocol will obtain informed consent. If an individual chooses to enroll, the consent form will be signed before participation begins. Once an individual joins the study and informed consent is obtained, the subject will receive a signed copy of the consent form. The subject may withdraw from the study at any time without repercussions to subsequent care.

If the patient is awake, alert, and oriented to person, place, and time, and demonstrates appropriate cognitive and communicative abilities as determined by the study coordinator or PI, the patient will be deemed to have the appropriate capacity to consent; however, given that borderline cognitive dysfunction and/or aphasia may not be easily distinguishable, the patient's

LAR/next of kin will be routinely included when consent to participate is being obtained for all subjects.

If it is determined that a patient is unable to consent for him/herself, due to a lack of capacity or lack of comprehension, consent will be sought from the patient's LAR/next of kin. Assent of the adult subject with LAR/next-of-kin will be obtained as appropriate. If such a subject regains his/her ability to make healthcare decisions, he/she will be given the opportunity to provide consent. This consent will be documented using the Addendum to Consent by Research Proxy for Continuing Participation in a Research Study form.

If the patient provides the consent delegate with assent to participate in the research but, due to a physical disability, is unable to sign the consent form, the patient will provide verbal consent and two witnesses and the patient's LAR/next of kin will sign the document affirming their presence during the consent process and the patient's physical disability as reason for an absent signature.

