Protection Against Risk:

Protection against tDCS-related risks: If any redness is apparent where the electrodes were placed, a cold compress will be offered to the subject. We will monitor subjects continually during the stimulation period, and will be in constant contact with the subjects. The study can be immediately stopped at the subject's request.

Protection of Confidentiality: To protect subjects' confidentiality, each subject will be assigned an ID number, and all data will be stored with the subject ID number only and not the subject's name. Data will be stored on a password-protected computer and on Feinstein's data server, REDCap. The *Feinstein Institute for Medical Research* will be used as a central location for data processing and management. Vanderbilt University, with collaboration from a consortium of institutional partners, has developed a software toolset and workflow methodology for electronic collection and management of research and clinical trial data. REDCap (Research Electronic Data Capture) data collection projects rely on a thorough study-specific data dictionary defined in an iterative self-documenting process by all members of the research team with planning assistance from the Biostatistics Unit of the *Feinstein Institute for Medical Research*. The iterative development and testing process results in a well-planned data collection strategy for individual studies. REDCap servers are housed in a local data center at the Feinstein and all web-based information transmission is encrypted. REDCap was developed specifically around HIPAA-Security guidelines and is recommended to Northwell Health researchers by both our Clinical Research Service, Research Compliance Office and Institutional Review Board. REDCap has been disseminated for use locally at other institutions and currently supports 965 active institutional partners and other institutions in 78 countries (www.project-redcap.org) Subject charts with medical history and assigned subject numbers will be kept in locked file cabinets stored at the Feinstein robot suite. Access to charts will be granted only to study investigators. Charts will be kept confidential and will not be shared with any third parties without permission from the subject. Any study data containing PHI that is transferred between investigators at Feinstein and collaborating institutes will be shared via encrypted email or encrypted storage drives.

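### Aims 2 and 3 cannot use a participant who leaves between the Phase I assessment and Visit 13, while Aim 1 keeps that person only if anodal came first; a mixed model on the change scores would use the data

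*Combined protocol and SAP*

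**What the plan says.** All three tests are named in Statistical Considerations and Data Analysis.

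- **Aim 1:** "A Wilcoxon signed-rank test will be used to compare naming accuracy scores pre and post anodal tDCS condition across participants".
- **Aim 2:** "This will be examined with a 2x2 repeated measures ANOVA for both treated and untreated items with stimulation type". The second factor is time, with levels T1 and T2, and both factors are within-person.
- **Aim 3:** an ANOVA on "change in naming performance in each stimulation condition (change in naming performance A-tDCS vs. S-tDCS) and severity level", so each person supplies two change scores.

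The Visit Schedule places the discharge evaluations at Visits 7 and 13 and the follow-up evaluations at Visits 8 and 14. The order of conditions is to be counterbalanced (Randomization).

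On leaving, Recruitment and Informed Consent says "The subject may withdraw from the study at any time without repercussions to subsequent care", and Protection Against Risk says "The study can be immediately stopped at the subject's request".

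The plan defines no analysis set, missing-data method, dropout allowance or replacement rule. It does not say whether outcome evaluations continue after someone stops stimulation, and it does not tie T1 and T2 to visits.

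**The concern.** The three aims do not need the same data. Someone who attends the Phase I evaluations and then leaves has given a complete change score for one condition. The tests named for Aims 2 and 3 have no way to use it, and whether Aim 1 uses it depends on the order to which the person was allocated.

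Three things follow. Aims 1 and 2 may be answered in different people. The order balance, which is the only protection against a period or practice effect because the ANOVA has no period term, can be lost. And if people leave because they gained little in Phase I, the completers' contrast is biased whenever leaving is more common, or more selective, in one order.

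**Working it through.** **Inputs.** The Visit Schedule gives the sample size: "In this pilot study, 24 participants will be accepted from our referral sources". Protection of Human Subjects gives 12 participants in total, so both are shown. The plan gives no SD, effect size, dropout rate or correlation. Assumptions: 1:1 order; change-score SD of 1; correlation 0.3 to 0.7 between a person's two changes; T2 taken as the discharge evaluation.

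**1. Who is usable, by order and time of loss**

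| Event | Anodal first | Sham first |
|---|---|---|
| Leaves after Visit 7 or 8, before Visit 13 | Aim 1 only | no aim |
| Leaves the study before Visit 7 | no aim | no aim |
| Misses Visit 7, returns for Phase II | no aim | Aim 1 only |
| Stops stimulation, still assessed | all aims | all aims |

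The first row is the point made here. A standard repeated-measures ANOVA routine, given data with one cell missing, stopped and reported unbalanced data. Dropping the person is therefore the practical default.

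**2. Expected numbers.** With d1 the loss before Visit 7 and d2 the loss between phases:

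- Aim 1: N/2 × (1 − d1) + N/2 × (1 − d1)(1 − d2)
- Aims 2 and 3: N × (1 − d1)(1 − d2)

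With d1 = 0 and d2 = 10% to 20%:

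- N = 24: 22.8 to 21.6 in Aim 1, and 21.6 to 19.2 in Aims 2 and 3.
- N = 12: 11.4 to 10.8 in Aim 1, and 10.8 to 9.6 in Aims 2 and 3.

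**3. Order imbalance, with no selective leaving.** Let π be the period effect (Phase II minus Phase I). The anodal-minus-sham difference carries −π in anodal-first participants and +π in sham-first participants. With 12 and 8 completers the pooled contrast carries (8 − 12)/20 = −0.20 π. Equal losses in the two orders would carry none.

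**4. Selective leaving, extreme one-sided case.** Suppose the 4 of 12 sham-first participants with the smallest sham gain leave, nobody else does, and the correlation is 0.5.

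- Mean sham gain of the remaining 8 rises by φ(0.431)/(2/3) = 0.545 SD. The exact expectation for the top 8 of 12 is 0.51.
- Their anodal gain rises by 0.5 × 0.545 = 0.27 SD.
- Their contrast shifts by −(0.545 − 0.27), about −0.27 SD.
- Pooled over 20 completers: −0.27 × 8/20 = −0.11 SD. With 0.51 it is −0.51 × 0.5 × 0.4 = −0.10 SD.

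**5. Selective leaving, same rule in both orders.** Simulation with about 19% leaving according to Phase I gain, and no period effect, gave bias of −0.008 to −0.014 SD for a true effect of 0.5 SD. It gave −0.019 to −0.036 SD for an effect of 0.8 SD with stronger dependence. Maximum likelihood on the correlated change scores left at most 0.006 SD in absolute value.

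**6. Precision.** Standard error of the anodal-sham effect at correlation 0.5:

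| N | Leave after Phase I | Completers only | Mixed model on changes | Ratio |
|---|---|---|---|---|
| 24 | 2 | 0.2132 | 0.2108 | 0.989 |
| 24 | 4 | 0.2236 | 0.2182 | 0.976 |
| 12 | 2 | 0.3162 | 0.3086 | 0.976 |

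Over correlations 0.3 to 0.7 the ratios run from 0.967 to 0.993, a gain of about 1% to 3%.

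**7. Which mixed model.** A random intercept on the raw naming scores makes a person's two changes uncorrelated. In the case of step 4 it in effect compares the mean observed anodal change with the mean observed sham change. The sham mean is then unbiased, and the anodal mean is raised by 8 × 0.27/20 = +0.11 SD. Simulation with attended-period scores agrees: bias moves from about −0.09 to about +0.11 SD. A mixed model on the change scores with condition and period terms leaves bias within about 0.03 SD, with almost the same standard error.

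**The case against.** This is a self-described pilot with about six weeks of participation. Complete-pair analysis of a short two-period cross-over is conventional, participants are blinded, and no dropout rate is given. Under symmetric dropout the bias is at most about 0.04 SD against a standard error of about 0.22 SD, which is less than a fifth of one standard error. The gain in precision is slight. All of that stands, and it keeps the point modest. It does not remove the order imbalance, which needs no selective leaving, or the mismatch between the aims.

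A reader might infer that anyone who stops stimulation early is lost from the ANOVAs. The documents do not say so. The Schedule Chart lists outcome measures in a separate row from tDCS, and the sentence on stopping at the participant's request sits under protection against tDCS risks. It is not a retention rule. But the discharge measures share a visit with the fifth training session, so the silence needs filling.

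A reader might also extend the Aim 1 pattern to every early loss. It fails for loss before Visit 7: someone who leaves the study then is out of all aims in either order, and someone who misses Visit 7 but returns for Phase II shows the reverse pattern.

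**Conclusion.** The point holds for loss between the Phase I assessment and Visit 13. Exclusion from Aims 2 and 3 follows from the tests named; the plan nowhere states a completers-only analysis or that data will be discarded, and it should not be read as saying so.

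The consequences are a different analysis set for Aim 1, exposure to a period effect (20% of it with 12 versus 8 completers), and possible selection bias. The bias is small under the assumed dropout. The figure near −0.1 SD needs a third of one order, exactly its poorest responders, to leave with no loss in the other, and should not be quoted as the expected size.

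Every magnitude rests on assumed dropout and correlation. The selective-leaving and imbalance examples also assume 24 participants, 12 per order; the conflict with the total of 12 given elsewhere must be reconciled. The change is worth making because it is cheap, not because the likely bias is large.

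**What to change.** - **Aim 2:** replace the ANOVA with a likelihood-based linear mixed model on the per-condition change in naming accuracy, separately for trained and untrained items. Use condition and period as fixed effects and a random participant effect. Include everyone with at least one condition measured, and state which visits define T1 and T2.
- **Aim 3:** use the same model with severity and its interaction with condition added.
- **Avoid** a model on raw scores with only a random intercept, for the reason in step 7 of the working.
- **Aim 1:** report the test as planned, and also in participants with both conditions measured.
- **Follow-up:** state that participants who stop stimulation or training but do not leave the study are invited to the outcome evaluations already scheduled. Record the date and reason for each exit.

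The cost is revised analysis wording, one sentence on continued evaluation and a short exit record, with no new visits. The downside is that the model assumes missingness depends only on observed scores; the exit reasons help to judge that.

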 - Condition 2 discharge outcome measures

Follow Up Testing Phase II

- Week 6, Visit 14 (approximately 60 minutes)
 - Condition 2 follow-up outcome measures

Schedule Chart

	Screen 1	Screen 2	Tx Condition 1		Cond 1 FU	Tx Condition 2		Cond 2 FU
	Visit 1	Visit 2	Visit 3-6	Visit 7	Visit 8	Visit 9-12	Visit 13	Visit 14
Informed Consent	X							
Medical Hx	X							
Medical FU		X						
Demographic Info	X							
Inclusion Criteria	X							
Neurological Exam	X							
Medication check	X							
Outcome Measures	X	X		X	X		X	X
tDCS and Aphasia tx			X	X		X	X	

Clinical Outcome Measures

Naming Probes (Primary Measure):

Picture naming accuracy will be assessed across two word lists, which were developed in a previous study (4). Each word list is comprised of a total of 75 trained and untrained nouns, which are controlled for word-frequency, semantic content, and word length, and depicted with color pictures presented on a laptop. Subjects will be provided with a different word list for each condition (sham vs. anodal tDCS), and asked to name each picture as soon as they see it. Responses will be audio/visually recorded for later transcription and scoring by an SLP. The first complete response will be used to determine the accuracy score. The outcome measure will be change in naming accuracy of trained items (task learning) and untrained items (learning generalization) in each condition.

Aphasia Battery (Secondary Measures):

A set of brief subtests from larger aphasia batteries will be used to assess changes in verbal expression and fluency in subjects with chronic expressive aphasia. Audio/Video recordings will be made of speech-language assessments for review and scoring by approved clinicians.

-“Diadochokinetic Rate” and “Increasing Word Length,” subtests of the Apraxia Battery for Adults (ABA-2): The ABA-2 is a valid and reliable measure of changes in motor speech across isolated speech sounds, multisyllabic utterances, and connected speech samples. Together, these subtests take approximately 5 minutes to administer and derive an apraxia impairment profile score (42, 45, 46).

-Generative Naming: Generative Naming is a commonly used clinical measure of verbal fluency and semantic memory in individuals with aphasia. It has been used frequently in the tDCS literature as a sensitive metric of changes in verbal fluency (38, 39, 43).

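### Aim 2 counterbalances stimulation order and word-list order but models neither, and the plan does not state that lists are crossed with stimulation: an efficiency loss, and a confounding risk left open

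*Combined protocol and SAP*

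**What the plan says.** Under Visit Schedule, the protocol balances two things: "Order of training word lists and tDCS stimulation condition will be counterbalance across participants". The Randomization section deals with stimulation order alone: "The order of anodal or sham stimulation will be counterbalanced across participants, and determined using a random number generator". It gives no rule for assigning lists and describes no joint order-by-list cells.

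Under Clinical Outcome Measures (Naming Probes), there are two lists, one per stimulation condition, with nouns "controlled for word-frequency, semantic content, and word length". The outcome is the change in naming accuracy within each condition, for trained and for untrained items.

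Under Statistical Considerations and Data Analysis, Specific Aim 2 is tested with a "2x2 repeated measures ANOVA for both treated and untreated items with stimulation type (A-tDCS,S-tDCS) and time (T1, T2) as factors". Neither period nor list appears in the model, and no section states that each list is used with both anodal and sham stimulation across participants. Enrolment is 24 under Visit Schedule and 12 under Protection of Human Subjects.

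**The concern.** Aim 2 is the direct anodal-versus-sham comparison on the primary measure, with 24 or 12 participants. Two things are at stake.

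- **Precision.** Balancing a factor and then leaving it out of the model keeps the estimate fair but leaves the factor's variation in the residual. The design has paid for the control and the analysis does not use it.
- **Possible confounding.** Balancing each order separately does not guarantee that lists are crossed with stimulation. If they are not, a difference between lists in how much participants gain cannot be told apart from the stimulation effect.

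**Working it through.** **Inputs.** From the documents: N = 24 or 12, two conditions, two lists, both orders counterbalanced, Aim 2 factors stimulation and time. The documents give no alpha, SD, target effect, period effect or list effect, and no power figure to reproduce. Assumed here: two-sided 5%, and a true effect of 0.6 at N=24 and 0.8 at N=12. All effects are in units of the SD of the paired anodal-minus-sham difference in change.

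**Model.** With two time points, the stimulation-by-time test is a paired t-test on D = change under anodal minus change under sham. Write

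D = τ + o·π + l·λ + e, with e ~ N(0,1),

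where o = +1 if anodal comes first and −1 otherwise; l = +1 if anodal is paired with list 1 and −1 if with list 2; π is the first-minus-second-period difference in gain; λ is the list 1-minus-list 2 difference in gain. A list that is harder by the same amount before and after training cancels in the change and does not enter.

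**Case 1: four balanced order-by-list cells.** The means of o, l and o·l are zero, so the mean of D is unbiased for τ with true variance 1/N. The planned test estimates that variance as s²/N, where E(s²) = 1 + (π² + λ²)·N/(N−1). At N=24:

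- π = λ = 0.5: 1 + 0.5 × 24/23 = 1.522, root 1.234. Allowing for critical values (2.069 on 23 df, 2.080 on 21 df), planned relative to adjusted interval width is 1.234 × 2.069/2.080 = 1.23.
- π = 0.25, λ = 0: 1 + 0.0625 × 24/23 = 1.065, root 1.032, width ratio 1.03.

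Simulation (100,000 runs per cell) compared the planned test (df N−1) with regression of D on o and l (df N−3):

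| Shifts (π, λ) | N=24 power, planned v adjusted | N=24 planned type I error | N=12 power, planned v adjusted | N=12 planned type I error |
|---|---|---|---|---|
| 0, 0 | 80.5 v 80.2% | 5.1% | 71.4 v 69.7% | 4.9% |
| 0.25, 0 | 78.7 v 80.2% | 4.4% | 69.1 v 69.6% | 4.5% |
| 0.25, 0.25 | 76.7 v 80.1% | 3.8% | 66.3 v 69.1% | 4.0% |
| 0.5, 0 | 72.8 v 79.9% | 2.8% | 62.2 v 69.6% | 3.0% |
| 0.5, 0.5 | 65.0 v 80.0% | 1.7% | 53.2 v 69.3% | 1.8% |

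Adjusted type I error is 4.9 to 5.1% throughout. The planned test is never anti-conservative here. By noncentral t with no shifts, the two lost degrees of freedom take power from 80.4 to 80.0% at N=24 and from 71.4 to 69.4% at N=12. Adjustment breaks even at a single shift of about 0.1 (N=24) or 0.2 to 0.25 (N=12).

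**Case 2: list tied to stimulation.** Take half the participants with anodal first and lists in order 1, 2, and half with sham first and lists in order 2, 1. Stimulation order is balanced and list order is balanced, yet anodal always gets list 1. Now l = +1 for everyone. The columns for intercept, o and l have rank 2, so the mean of D estimates τ + λ and no list term can separate them. With τ = 0 and no period shift, noncentral t gives a significant result in 7.6, 21.7 or 65.0% of trials at N=24 for λ = 0.1, 0.25 or 0.5, and 6.2, 12.4 or 35.3% at N=12. The aliasing needs no assumed effect size; these percentages do.

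**Dropout, N=12, blocked.** With no shift, planned v adjusted power is 67.0 v 63.6% with 1 of 12 lost and 61.6 v 56.9% with 2 lost. With one 0.25 shift it is 65.1 v 64.2% and 59.0 v 56.7%, so adjustment loses. With both shifts at 0.25 it gains 1.8 and 0.6 points. At N=24 with 2 lost and one 0.25 shift, adjustment still helps (74.5 v 75.7%).

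**The case against.** The strongest reply is that on the natural reading nothing is wrong with validity, and the rest is a preference about efficiency in a self-described pilot. Naming list order and stimulation order as two things to balance suggests they vary separately; if each list stayed with one condition, list order would follow from stimulation order and naming both would be redundant. The nouns are matched on three properties, the outcome is change, and nothing in the documents supports shifts as large as 0.5 SD. At N=12, small shifts and one or two dropouts can wipe out the gain.

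Most of this stands. It limits the point to efficiency plus an unclosed gap. It does not remove the gap: the wording is satisfied by the tied layout, and matching on word properties is not a statement that the two lists are equally learnable.

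Three stronger readings are tempting and are not supported:

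- **That the planned test is biased or inflates type I error.** Under balanced crossing it does neither; it is conservative.
- **That the trial ties each list to one condition.** The text permits this but does not say it.
- **That allocation is by unrestricted coin flips.** The Randomization sentence promises counterbalancing as well as a random number generator; only the method of reaching balance is unstated.

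**Conclusion.** The point holds as an efficiency improvement plus a safeguard against list confounding, not as a demonstrated bias. Under balanced crossing, leaving out both terms makes the interval too wide whenever gain differs appreciably by period or by list. At N=24 the loss runs from about 1.5 points of power (one 0.25 SD shift) to 15 (two 0.5 SD shifts); at N=12 it is about 0.5 points for one 0.25 SD shift and can reverse with dropout. These sizes rest wholly on assumed shifts and effects. The tied layout is the less natural reading, but if it were used, a list difference in gain would pass in full into the anodal-versus-sham contrast, and this could not be repaired after the data are collected. That is why it is worth settling at allocation.

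**What to change.** Adopt as one package:

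1. State that each list is used with both anodal and sham stimulation across participants.
2. Allocate in equal blocks over the four order-by-list cells: 6 per cell at N=24, 3 per cell at N=12. The two enrolment figures need reconciling, but both divide evenly.
3. Analyse change in naming accuracy, separately for trained and untrained items, with stimulation, period and word list as fixed effects and participant as a random effect. Report the stimulation effect with a 95% CI. Order must enter as a period effect on change; a between-participant sequence term alone does not adjust the contrast.

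The parts belong together. Without crossing, the list term may not be estimable, and one term alone leaves the other factor in the error.

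The cost is two residual degrees of freedom (23 to 21, or 11 to 9). With no shifts this is about 0.3 points of power at N=24 and 2 at N=12, rising at N=12 to 3.4 points with one dropout and 4.7 with two. No visits or participants are added. The change does not address carry-over across the one-week gap.
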